### 9.4.2 Immunogenicity analyses

**Table 6 - Immunogenicity analyses**

Endpoint	Statistical Analysis Methods
Secondary: Number of participants with treatment-emergent AIA during the 16-week treatment	
Immunogenicity analyses will be based on the AIA population. Only AIA results from samples collected during the on-treatment period and at least 8 hours after the last administration of meal-time insulin will be taken into account in the analysis.
 
For descriptive purpose, the difference between the switching arm and the non-switching arm in the percentage of participants with treatment-emergent AIAs (AIA incidence) will be provided with associated 2-sided 90% CI. Results will be obtained by fitting a binomial regression model with an identity-link function. The model will include fixed categorical effects for the treatment group and randomization strata. The risks within each treatment group and risk difference will be provided with their 90% CI using the adjusted least squares mean estimates of the treatment effect.

AIA: anti insulin aspart antibody; IMP: investigational medicinal product

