## 4 STUDY DESIGN

### 4.1 OVERALL DESIGN

This is a randomized, open-label, active-controlled, 2-arm parallel-group multicenter Phase 3 trial in adults with T1DM also using insulin glargine.

Upon confirmation of eligibility based on the screening procedures, participants who have not been on NovoLog and insulin glargine (100 U/mL) for at least 12 weeks before screening will complete a run-in period of up to 12 weeks during which they will be administered NovoLog and Lantus. Run-in period duration will be such that, at the time of randomization, the participants have been on NovoLog and insulin glargine (100 U/mL) for at least 12 weeks.

Participants will be randomized 1:1 to 4x4-week periods alternating use of SAR341402 and NovoLog (starting with NovoLog in the first treatment period and receiving SAR341402 during the last of the 4 treatment periods, “switching arm”) or 16 weeks continuous use of NovoLog (“non-switching arm”); see flow-chart in [Section 1.2](#).

Randomization will be stratified by HbA1c (<8.0%, ≥8.0%) obtained at the screening visit (Visit 1).

Insulin glargine 100 U/mL (Lantus) will be administered as mandatory background therapy throughout the treatment period of the study.

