#### **9.4.4 Other analyses**

Other AIA endpoints will be derived from AIA assessments (status, titer) as follows:

- a Participants with treatment-induced AIAs will be defined as participants with AIAs that developed de novo (seroconversion) following the IMP administration.
- b Participants with treatment-boosted AIAs will be defined as participants with pre-existing AIAs that were boosted to a significant higher titer following the IMP administration (at least 4 fold increase in titer values).
- c Participants with treatment-emergent AIAs (AIA incidence) will be defined as participants with treatment-induced or treatment-boosted AIAs.

Analysis of tertiary/exploratory endpoints (other AIA endpoints, clinical effects of AIA, change in insulin dose, and efficacy analyses) will be described in the statistical analysis plan finalized before database lock.

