### **2.1.4 Immunogenicity variables**

As per protocol, only the number of patients with treatment-emergent anti-insulin aspart antibodies (AIA) during the 16-week treatment period is secondary. All other immunogenicity endpoints are tertiary/exploratory.

If a patient discontinues the treatment prematurely, the process described in [Section 2.5.1](#) will be applied to retrieve immunogenicity assessments performed at the end of treatment visit (Visit 8000).

AIA measurements will be performed in a blinded fashion at a central laboratory (see study flowchart in Section 1.3 of the protocol) using a validated anti-insulin aspart antibody binding assay methodology. Only AIA results from samples collected during the on-treatment period and at least 8 hours after the last administration of mealtime insulin will be taken into account in the analysis.

Anti-insulin aspart antibodies evaluation will consist of:

- Anti-SAR341402/ NovoLog antibody positive/negative status
- Anti-SAR341402/ NovoLog antibody titer
- Cross-reactivity to human insulin positive/negative status

The following definitions will be used to identify patients with a change in AIA response during the on-treatment period (see [Section 2.1.4](#) (1) :

- **Patients with treatment-induced AIAs** will be defined as patients with AIAs that developed de novo (seroconversion) following the IMP administration (ie, patients with at least one positive AIA sample at any time during the on-treatment period, in those patients without pre-existing AIA or with missing sample at baseline).
- **Patients with treatment-boosted AIAs** will be defined as patients AIA positive at baseline that were boosted to a significant higher titer following the IMP administration (ie, patients with at least one AIA sample with at least a 4-fold increase in titers compared to baseline value at any time during the on-treatment period, in those patients with preexisting AIA). The 4-fold increase in titer corresponds to an increase of two dilution steps within the titration experiment. A single dilution difference (2-fold titer increase) is within the expected imprecision of the titration method and is therefore not considered a relevant change.

Patients with treatment-emergent AIA (Yes, No, Inconclusive) will be derived as follows:

- Patients with treatment-emergent AIAs (AIA incidence) will be defined as patients with treatment-induced or treatment-boosted AIAs.

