#### *Anti-insulin antibody response*

The number and percentage of patients will be provided by treatment group for each of the following categories:

- Patients with treatment-induced AIAs,
- Patients with treatment-boosted AIAs,
- Patients with treatment-emergent AIA (AIA incidence),
- Patients without treatment-emergent AIA,
- Patients with pre-existing AIAs or treatment-induced AIAs (AIA prevalence).

For exploratory purposes, the difference between the switching arm and the non-switching arm in the percentage of patients with treatment-emergent AIAs (AIA incidence) will be provided with associated 2-sided 90% CI. Patients with inconclusive results will not be part of the analysis. Results will be obtained by fitting a binomial regression model with an identity-link function. The model will include fixed categorical effects for treatment and the randomization stratum of screening HbA1c (<8%, ≥8%). If the model does not converge (e.g., due to sparse data), randomization strata may be removed from the model. The risks within each treatment group and risk difference will be provided with their 90% CIs using the adjusted LS mean estimates of the treatment effect.

For patients with treatment-induced and treatment-boosted AIAs, the peak titer will be described using median, Q1 and Q3.

The number and percentage of patients with treatment-induced, treatment-boosted and treatment-emergent AIAs will also be presented by visit in each treatment group using tables and/or graphs.

Boxplots of the peak AIA titer will be presented by treatment group and according to the treatment-emergent AIA status (Yes, No). These graphs will be used to identify AIA ‘outliers’, defined as peak AIA titers higher than the boxplot upper whiskers (ie, higher than 1.5 times the interquartile range above the third quartile).

A listing with inconclusive patients will be provided.

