### ***Subgroup analyses***

Exploratory analyses will be performed by the subgroups defined by the Anti-SAR341402/NovoLog antibody status at baseline (Positive, Negative), and by COVID-19 impact (Non-impacted, Impacted; see subgroup definition in [Section 2.2](#)). The second subgroup analysis will be performed only if the number of patients is sufficient. Further subgroup analyses may be performed if deemed necessary for interpretation of results.

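### The treatment-emergent antibody risk difference is adjusted for HbA1c stratum only, although baseline antibody status sets each participant's counting rule; a stratified estimate should be prespecified beside it

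*Protocol*

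**What the plan says.** Protocol Table 6 names the secondary endpoint, "Number of participants with treatment-emergent AIA during the 16-week treatment", and estimates the arm difference in percentage with a 2-sided 90% CI from a binomial regression with identity link. On covariates it says: "The model will include fixed categorical effects for the treatment group and randomization strata". SAP 2.4.6.1 (Anti-insulin antibody response) repeats this: "The model will include fixed categorical effects for treatment and the randomization stratum of screening HbA1c". It lets the stratum be removed if the model does not converge. Protocol 4.1 gives the only stratification factor: "Randomization will be stratified by HbA1c (<8.0%, ≥8.0%) obtained at the screening visit (Visit 1".

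The endpoint joins two events. Under SAP 2.1.4, one positive on-treatment sample counts as treatment-induced AIA "in those patients without pre-existing AIA or with missing sample at baseline". A participant positive at baseline counts only if the antibodies were "boosted to a significant higher titer following the IMP administration (at least 4 fold increase in titer values" (Protocol 9.4.4). Baseline AIA is sampled at Visit 3 under both schedules of activities.

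Baseline status is used elsewhere. Protocol Table 2 lists induced and boosted AIA as separate exploratory endpoints, each with its own baseline-status denominator. SAP 2.4.6.1 tabulates both by arm and adds a subgroup analysis: "Exploratory analyses will be performed by the subgroups defined by the Anti-SAR341402/NovoLog antibody status at baseline (Positive, Negative". Protocol Table 6 presents the risk difference as descriptive, and the SAP calls it exploratory. There is no margin, test or power statement for it.

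**The concern.** The variable that decides which rule applies to a participant is known before treatment, is not balanced by design, and is absent from the model. The variable that is in the model, screening HbA1c, plays no part in the endpoint's definition. If the two rules produce events at different rates and one arm happens to hold more baseline-positive participants, the overall difference moves for a reason unrelated to switching. Adjusting for HbA1c cannot undo that.

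This is the plan's only between-arm immunogenicity estimate with a CI, and the study rationale (Protocol 2.1) turns on whether switching raises the immune response. With no test attached, readers will rely on the estimate itself. An adjustment chosen after an imbalance has been seen would be post hoc.

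**Working it through.** **The plan's own figures.** No AIA prevalence, event rate or power is stated. The only sample-size figure concerns PK: 73 evaluable per arm, log-scale SD 0.35, true ratio 0.95-1.05, at least 90% power. It reproduces (two one-sided tests, t-based: 0.903 at 0.95 and 0.910 at 1.05) but says nothing about antibodies.

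**Inputs.** From the documents: about 184 randomized 1:1, so n = 92 per arm. Assumed: baseline-positive share q = 20%, 40% or 60%; event rate pN in baseline negatives and pP in baseline positives; no true arm effect.

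**1. Shift.** With no arm effect, the expected unadjusted difference given the baseline split is (q1 - q2) x (pP - pN). It is zero if the two rates are equal, and its sign follows the sign of the gap. The HbA1c term leaves this unchanged if HbA1c is unrelated to AIA status.

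**2. How often an imbalance occurs.** SD of q1 - q2 = sqrt(2q(1-q)/n).
- q = 20%: sqrt(2 x 0.2 x 0.8/92) = 5.9 points
- q = 40% or 60%: sqrt(2 x 0.4 x 0.6/92) = 7.2 points

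Ten points of 92 is 9.2 people, so 10 or more. With a continuity correction the cut is 9.5/92 = 10.3 points.
- q = 20%: z = 10.3/5.9 = 1.75, so 8% of trials (both directions)
- q = 40% or 60%: z = 10.3/7.2 = 1.43, so 15%

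**3. Shift in those trials.** The mean imbalance, given an excess beyond the cut, is SD x phi(z)/(1 - Phi(z)): 12.7 points at q = 20% and 13.6 points at q = 40% or 60%.

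| Gap between pN and pP | Mean shift, points |
|---|---|
| 10 | 1.3-1.4 |
| 15 | 1.9-2.0 |
| 25 | 3.2-3.4 |

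Simulation agrees: about 2 points for rates 20%/5% and 3.2 to about 3.5 for 30%/5%. A Mantel-Haenszel difference stratified by baseline status averages within 0.1 point of zero in the same trials.

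**4. Precision.** Share of variance removed = q(1-q)(pP - pN)^2 / [p(1-p)], with p = q x pP + (1-q) x pN. The 90% half-width is 1.645 x sqrt(2p(1-p)/92).

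| q | pN / pP | p | Variance removed | SE reduction | 90% half-width, points |
|---|---|---|---|---|---|
| any | 10% / 10% | 0.10 | 0% | 0% | 7.28 to 7.28 |
| 0.2 | 15% / 5% | 0.13 | 0.16 x 0.01/0.1131 = 1.4% | 0.7% | 8.16 to 8.10 |
| 0.3 | 25% / 5% | 0.19 | 0.21 x 0.04/0.1539 = 5.5% | 2.8% | 9.51 to 9.25 |
| 0.6 | 30% / 5% | 0.15 | 0.24 x 0.0625/0.1275 = 11.8% | 6.1% | 8.66 to 8.13 |

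**5. Cost when it is not needed.** With equal rates (10%/10%) and four strata (AIA status by HbA1c), the simulated SD rises by under 1%. At the smallest gap above, this cost roughly cancels the gain.

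**6. Sample size.** At 73 per arm the SD of the imbalance is 6.6 points (q = 20%) to 8.1 points (q = 40%), so imbalances of 10 points are somewhat more frequent.

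**The case against.** The strongest reply is that no decision rests on this number. It is descriptive, and its interval already allows for chance imbalance on average. A shift of 3.4 points also sits well inside a half-width of about 9.7 points (q = 40%, 30%/5%). That stands, and it limits the point to a modest one. It does not remove it: among simulated trials with an imbalance of 10 points or more, the unadjusted 90% interval covered 84-88%, so the allowance is weaker in the trials where a reader would see the imbalance.

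Three stronger readings are tempting, and the documents do not support them.
- *A reader might infer that the planned estimate is biased.* Randomization keeps it unbiased over repeated trials. This is a matter of conditional balance and some efficiency.
- *A reader might infer that the plan ignores baseline antibody status.* It reports induced and boosted counts separately with baseline-status denominators, reports AIA status at baseline, and commits to the baseline-status subgroup. These would expose an imbalance. None of them corrects the overall difference.
- *A reader might infer that one positive sample is the easier rule, or that precision is given up for free.* Neither can be shown. All participants have had at least 12 weeks of NovoLog before randomization, so baseline negatives have been exposed and are still negative. The gap could be small or reversed, and the gain ranges from nothing to modest.

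Convergence is also a fair objection to adding a term to the identity-link model. In a plain iterative fit the extra term raised failed or boundary fits. SAS may do better, so only the direction is reliable. A Mantel-Haenszel estimate needs no iterative fit.

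**Conclusion.** The point holds as a limited one. The overall treatment-emergent AIA risk difference omits the baseline variable that sets each participant's counting rule, and no planned analysis adjusts the overall figure for it. If event rates under the two rules differ by 10 to 25 points, an imbalance of at least 10 points, expected in 8-15% of trials with 92 per arm, moves the estimate by about 1 to 3.5 points in either direction. Adjustment then lowers the standard error by about 1-6%, less at the small end once the cost of stratifying is counted. If the rates are equal, there is nothing to correct and the cost is under 1%.

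All of these sizes rest on assumed rates. They also assume that few participants change arm under the as-treated rule of SAP 2.3.2 and 2.3.3. The primary PK conclusion is not affected.

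**What to change.** In SAP 2.4.6.1, before database lock, prespecify a Mantel-Haenszel risk difference for treatment-emergent AIA with its 90% CI, stratified by baseline AIA status and HbA1c stratum, and report it alongside the planned identity-link model. Define the baseline classes as positive versus negative or missing, which follows the induced and boosted definitions in SAP 2.1.4 and needs no separate rule for missing baselines. Leave inconclusive patients out, as already planned, and name the variance estimator.

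Do not drop the HbA1c stratum in favour of baseline AIA status: it is the randomization stratum, and both can be kept. Do not add baseline status to the identity-link model, where it may worsen convergence.

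The cost is a few lines of SAP text and one extra estimate, with no new data. If the two event rates turn out similar, the second estimate will add little.

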### 9.4.3 Safety analyses

All safety analyses will be descriptive and performed on the Safety Population.

The **observation period for safety data** is divided into 3 main segments:

- The pre-treatment period is defined as the time from informed consent up to the time of the first injection of IMP.
- The on-treatment period is defined as the time from the first injection of IMP up to 1 day after the last injection of IMP.

- The post-treatment period is defined as the time starting 1 day after last injection of IMP (after the on-treatment period).

The AE observations will be classified per the observation periods of safety data as defined above:

- **Pre-treatment AEs** are AEs that developed or worsened or became serious during the pre-treatment period.
- **Treatment-emergent AEs** are AEs that developed or worsened or became serious during the on-treatment period.
- **Post-treatment AEs** are AEs that developed or worsened or became serious during the post-treatment period.

Analyses will focus on safety observations during the on-treatment period.

The baseline value for safety variables will be defined as the last available value prior to the first injection of IMP.

**Table 7 - Safety analyses**

Endpoint	Statistical Analysis Methods
Secondary: Number of participants with at least one hypoglycemic event for the 16-week treatment period	Proportions of participants with at least one hypoglycemic event will be presented overall and by type of event for each treatment group.
Secondary: Number of hypoglycemic events per participant-year for the 16-week treatment period	
Incidences of hypoglycemia per participant-year will be computed as: <math>365.25 \times (\text{number of episodes of hypoglycemia}) / (\text{number of days exposed})</math> and summarized overall and by type of event for each treatment group.
 
For exploratory purpose, odds-ratios and rate ratios of hypoglycemic event may be provided for SAR341402/NovoLog switching group versus NovoLog non-switching group, overall and for some categories of hypoglycemia. Details will be provided in the SAP.
 
Further analyses (eg, by subgroup, over time) may be done as appropriate and will be detailed in the SAP.

Secondary: Number of participants with AE for the 16-week treatment period	
All AEs will be coded using the version of MedDRA currently in use by the sponsor at the time of database lock.
 
Adverse event incidence tables will present using the MedDRA hierarchy, the number and percentage of participants experiencing an AE for each treatment group.
 
Adverse event incidence table will be provided by treatment group for all types of TEAEs: all TEAEs, all treatment-emergent SAEs, all TEAEs leading to definitive treatment discontinuation and all TEAEs leading to death.
 
The number and proportion of participants with injection site and hypersensitivity reactions (identified by MedDRA search) will also be summarized by treatment group, and events adjudicated as possible hypersensitivity reactions by the ARAC will be described.

AE: adverse event; MedDRA: Medical Dictionary for Regulatory Activities; SAE: serious adverse event; TEAE: treatment-emergent adverse event

#### **9.4.4 Other analyses**

Other AIA endpoints will be derived from AIA assessments (status, titer) as follows:

- a Participants with treatment-induced AIAs will be defined as participants with AIAs that developed de novo (seroconversion) following the IMP administration.
- b Participants with treatment-boosted AIAs will be defined as participants with pre-existing AIAs that were boosted to a significant higher titer following the IMP administration (at least 4 fold increase in titer values).
- c Participants with treatment-emergent AIAs (AIA incidence) will be defined as participants with treatment-induced or treatment-boosted AIAs.

Analysis of tertiary/exploratory endpoints (other AIA endpoints, clinical effects of AIA, change in insulin dose, and efficacy analyses) will be described in the statistical analysis plan finalized before database lock.

#### **9.5 INTERIM ANALYSES**

No interim analysis is planned.

##### **9.5.1 Data Monitoring Committee (DMC)**

Not applicable.

## **10 SUPPORTING DOCUMENTATION AND OPERATIONAL CONSIDERATIONS**

### **10.1 APPENDIX 1: REGULATORY, ETHICAL, AND STUDY OVERSIGHT CONSIDERATIONS**

#### **10.1.1 Regulatory and Ethical Considerations**

- This study will be conducted in accordance with the protocol and with the following:
  - Consensus ethical principles derived from international guidelines including the Declaration of Helsinki and Council for International Organizations of Medical Sciences (CIOMS) International Ethical Guidelines,
  - Applicable International Conference on Harmonization (ICH) Good Clinical Practice (GCP) Guidelines,
  - Applicable laws and regulations.
- The protocol, protocol amendments, ICF, Investigator Brochure, and other relevant documents (eg, advertisements) must be submitted to an IRB/IEC by the Investigator and reviewed and approved by the IRB/IEC before the study is initiated.
- Any amendments to the protocol will require IRB/IEC approval before implementation of changes made to the study design, except for changes necessary to eliminate an immediate hazard to study participants.
- The Investigator will be responsible for the following:
  - Providing written summaries of the status of the study to the IRB/IEC annually or more frequently in accordance with the requirements, policies, and procedures established by the IRB/IEC,
  - Notifying the IRB/IEC of SAEs or other significant safety findings as required by IRB/IEC procedures,
  - Providing oversight of the conduct of the study at the site and adherence to requirements of 21 Code of Federal Regulations (CFR), ICH guidelines, the IRB/IEC, European regulation 536/2014 for clinical studies (if applicable), and all other applicable local regulations.

#### **10.1.2 Financial disclosure**

Investigators and sub-Investigators will provide the Sponsor with sufficient, accurate financial information as requested to allow the Sponsor to submit complete and accurate financial certification or disclosure statements to the appropriate regulatory authorities. Investigators are responsible for providing information on financial interests during the course of the study and for 1 year after completion of the study.

### 10.1.3 Informed Consent Process

- The Investigator or his/her representative will explain the nature of the study to the participant or his/her legally authorized representative and answer all questions regarding the study.
- Participants must be informed that their participation is voluntary. Participants will be required to sign a statement of informed consent that meets the requirements of 21 CFR 50, local regulations, ICH guidelines, Health Insurance Portability and Accountability Act (HIPAA) requirements, where applicable, and the IRB/IEC or study center.
- The medical record must include a statement that written informed consent was obtained before the participant was enrolled in the study and the date the written consent was obtained. The authorized person obtaining the informed consent must also sign the ICF.
- Participants must be re-consented to the most current version of the ICF(s) during their participation in the study.
- A copy of the ICF(s) must be provided to the participant or the participant's legally authorized representative.

Participants who are rescreened are required to sign a new ICF.

